**STUDY SYNOPSIS**

**Research Questions:**

1. Among patients with metastatic solid tumours in each of three pre-defined cohorts (A, B, C), what proportion of patients have a positive cytology, a positive circulating tumour DNA (ctDNA), and/or positive circulating tumour cells (CTC) in cerebrospinal fluid (CSF) samples?
2. Among the patients enrolled in the study, how do ctDNA and CTC results obtained from cerebral spinal fluid (CSF) and plasma compare in each of three cohorts (A, B, C)?
3. Is it feasible to perform proteomic analysis of CSF among patients with metastatic solid tumours who have at least one positive CSF biomarker (cytology and/or ctDNA and/or CTCs) in each of three cohorts (A, B, C)?

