**End points:**

1. Primary endpoint: Proportion of eligible patients with positive CSF cytology, positive ctDNA, and positive CTCs.
2. Secondary endpoint: Concordance of mutations identified on CSF ctDNA with plasma ctDNA.
3. 3. Exploratory endpoint: Feasibility of conducting proteomic analysis of CSF.

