**Secondary Objectives**

1. The concordance of mutations identified based on ctDNA profiling in the CSF and blood plasma in each of three cohorts (A, B, C).
2. To explore the feasibility of proteomic analysis using CSF samples in each of three cohorts (A, B, C).

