## 7. STATISTICAL ANALYSIS

### **Planned Cytological Analysis:**

CSF and blood plasma samples will undergo proteomic and cytological analysis using the genomic equipment at the Sunnybrook Research Institute (SRI). While the specific platform has yet to be finalized, technologies such as Next Generation Sequencing (NGS), the QX200 Droplet Digital PCR System, and ANGLE plc's Parsortix® system are under consideration for their suitability in cytological and proteomic applications.

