### **Planned Statistical Analysis:**

For the first objective, binary data will be analyzed to determine the proportion of positive CSF samples from the total number of samples collected. These proportions will then be stratified by tumour type for comparison. The second objective is comparing ctDNA detection in CSF and blood plasma samples. This will involve observing the unique and shared mutations across sample types, and ultimately summarizing findings in a concordance table. From the table, test performance metrics such as sensitivity and specificity will also be derived. The third objective evaluates the feasibility of proteomic analysis and will be measured by the proportion of CSF samples that yield sufficient protein concentrations. The mean number of proteins detected per samples and any commonalities will be reported. All statistical analysis will be conducted using Excel and R. Given the exploratory nature of the study, graphical illustrations and plots will be emphasized over hypothesis testing with p-value.

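### Proteomic feasibility is measured by whether the CSF holds enough protein, which is an upper limit on whether the analysis can be performed

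*Protocol*

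**What the plan says.** The synopsis of the protocol puts the third research question as "Is it feasible to perform proteomic analysis of CSF among patients with metastatic solid tumours who have at least one positive CSF biomarker", to be answered in each of cohorts A, B and C. The third end point in the synopsis is "Feasibility of conducting proteomic analysis of CSF", labelled exploratory. Section 1 lists the same aim among the secondary objectives, again by cohort. All three places concern carrying out the analysis.

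Section 7, under Planned Statistical Analysis, then fixes the measure: feasibility "will be measured by the proportion of CSF samples that yield sufficient protein concentrations". The next sentence adds a description: "The mean number of proteins detected per samples and any commonalities will be reported". No threshold for enough protein is given, and nothing defines a successful proteomic run.

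On the laboratory side, the paragraph on cytological and proteomic analysis in Section 7 says "While the specific platform has yet to be finalized", and Section 6 makes part of the biomarker work depend on outside collaborations for which agreements must first be obtained.

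**The concern.** The question is whether the analysis works; the measure is whether the specimen is adequate for it. Enough protein may be needed for a proteomic profile, but it does not guarantee one. The run may not take place, may fail, or may give data of unusable quality, and none of these outcomes enters the proportion.

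This matters here because the platform is still open, so whether the assay performs on these CSF samples is the main unknown. A reader planning follow-on work would take the feasibility proportion as the answer to research question 3, although it leaves out that step.

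This is not a detail left for a statistical analysis plan. The protocol states how feasibility will be measured, and an analysis plan that followed it faithfully would carry the mismatch forward.

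**Working it through.** **Inputs.** The target comes from research question 3 and the third end point in the synopsis. The measure and the accompanying protein count come from Section 7. The planned cohort size is 20 (Section 3). The protocol gives no expected share of samples with enough protein, no expected run-success rate and no feasibility threshold, so there is no figure of its own to reproduce.

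**Step 1: the two quantities.** Let n be the CSF samples in the denominator, a those with enough protein, and c those among the a whose run completes and passes a quality criterion, so that 0 ≤ c ≤ a.

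- Measure in Section 7: a/n
- Quantity asked about: c/n
- Gap: (a − c)/n, which is never negative

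The number c does not appear in a/n. The stated proportion therefore stays fixed while c moves anywhere between a and 0.

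**Step 2: illustration.** Take n = 20 (the full planned cohort) and assume a = 18. Intervals are exact (Clopper-Pearson) 95%.

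| Successful runs c | Stated measure a/n | Run-based measure c/n |
|---|---|---|
| 18 | 18/20 = 90% (68.3% to 98.8%) | 18/20 = 90% (68.3% to 98.8%) |
| 14 | 90% (same interval) | 14/20 = 70% (45.7% to 88.1%) |
| 9 | 90% (same interval) | 9/20 = 45% (23.1% to 68.5%) |
| 0 | 90% (same interval) | 0/20 = 0% (0% to 16.8%) |

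The value of a does not drive the result. With c = 0 and a = 10, 15, 18 or 20, the stated measure is 50%, 75%, 90% or 100%, and the run-based measure is 0% each time.

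**Step 3: does the average protein count fill the gap?** Suppose that each successful run detects K proteins.

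- If the average is taken over samples that gave data, it is K for c = 18, 14 or 9. Partial failure does not show.
- If failed runs among the 18 adequate samples count as zero, the average is K × c/18. With c = 9 it is K × 9/18 = K/2, the same as 18 successful runs that each detect K/2. The average alone cannot separate fewer successful runs from a lower yield per run.
- If c = 0, no proteins are detected under either convention, and the failure is plain.

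The count therefore exposes total failure but does not recover c/n.

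**Step 4: the denominator.** Research question 3 restricts the proteomic question to patients with at least one positive CSF biomarker. Section 7 speaks of CSF samples without that restriction, and the end point and the Section 1 objective do not repeat it. The number of biomarker-positive patients per cohort is not given and may be below 20, notably in the control cohort. The identity in Step 1 holds for any n, but each failed run weighs more when n is smaller: 1/20 = 5 percentage points, against 1/10 = 10 points if only 10 patients were positive (an assumed number).

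**The case against.** The strongest reply is that the proportion is not the only thing reported under this objective. Section 7 also promises the average protein count and commonalities, which are outputs of the assay. A reader might infer that a complete failure of the proteomic work would go unseen; the protocol does not support that, because there would then be no proteins or commonalities to report. What stands against this reply is Step 3: the count carries no success criterion and does not give the proportion of samples successfully analysed.

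A second reply is that the wording could mean concentrations produced by the proteomic run itself, since the protocol does not say when or by which assay they are measured. That reading is possible. The plainer one is specimen adequacy, because detected proteins are named separately in the next sentence. If the sponsor meant assay output, the sentence still needs to say so.

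A third reply is that the endpoint is exploratory and the study descriptive, with plots preferred to hypothesis tests. This is correct and limits the weight of the point: the primary endpoint and the mutation concordance are unaffected. It is also why one should not go on to calculate how often the stated measure would pass some feasibility bar. The protocol sets no bar, and such a calculation would describe a decision that the study does not make.

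**Conclusion.** The point holds in a limited form. The feasibility proportion in Section 7 measures specimen adequacy and is an upper limit on the feasibility that research question 3 asks about. It overstates feasibility by (a − c)/n, the share of samples with enough protein but no successful run. The protocol gives no basis for estimating that share: in the illustration the overstatement runs from 0 points (18 successful runs of 18) through 20 points (14) and 45 points (9) to 90 points (none).

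The conclusion rests on reading enough protein as a property of the specimen, and on a successful run requiring enough protein. The illustration also assumes 18 adequate samples and a full cohort of 20, which the restriction to biomarker-positive patients may not leave. Total failure would be visible elsewhere in the report; partial failure could be missed. The matter should be corrected, but it concerns an exploratory endpoint and does not touch the primary analysis.

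**What to change.** In Section 7, under Planned Statistical Analysis:

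- **Numerator:** CSF samples that complete the proteomic run and pass a quality criterion. The criterion cannot be written now because the platform is open; state that it will be set once the platform is chosen and before the first sample is run.
- **Denominator:** all CSF samples from the patients named in research question 3 (at least one positive CSF biomarker), separately for each cohort, with failed or unrun samples counted as not feasible.
- **Preceding step:** report the proportion with enough protein beside it, on the same denominator, so that losses from inadequate specimens can be told apart from losses in the assay.

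The cost is a few sentences of text. No patients, samples or procedures are added, since the proteomic runs and the protein counts are already planned. The downside is that the reported feasibility figure can only stay the same or fall relative to the proportion with enough protein.
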